## **9. STUDY ASSESSMENTS**

The procedures and assessments that will be conducted during this study are described in this section and summarized in the Schedule of Assessments ([Table 5](#)). Detailed instructions regarding all laboratory procedures, including collection and handling of samples, will be included in the study Laboratory Manual provided by the Sponsor or its designee.

Informed consent must be granted by each subject/next of kin/legal proxy according to hospital procedures and local regulations prior to the initiation of any study procedure or assessment (other than those considered SOC).

**Table 5: Schedule of Assessments**

Visit	Screening	Baseline/ Treatment	Continued Treatment	Follow-up Visits					Early Term/ End of Study Visit
Day	-1a	1a	2	3	7 ± 1	14 ± 2	28 ± 2	60 ± 2	90 ± 4
Informed consent	X								
Eligibility assessment	X	X							
Randomization if appropriate		X							
Medical history/signs and symptoms	X	X b							
WHO Severity Score c	X	X	X	X	X	X	X	X	X
Sputum culture d, e	X								
Blood or urine pregnancy	X (for women of childbearing potential only)						X		X (for women of childbearing potential only)
HIV	Not required (can be done at the discretion of caregivers)								
Confirm COVID-19 pneumonia (CXR or CT, RT-PCR for COVID-19) e, f	X					X	X		
CURB-65 score	X			X	X	X	X	X	
Physical exam g	X	X b	X	X	X	X	X	X	X
Abbreviated Mental Test Score	X			X	X	X	X	X	

Visit	Screening	Baseline/ Treatment	Continued Treatment	Follow-up Visits					Early Term/ End of Study Visit
Day	-1a	1a	2	3	7 ± 1	14 ± 2	28 ± 2	60 ± 2	90 ± 4
Vital signs, including pulse oximetry h	X	X	X	X	X	X	X	X	X
EKG e, i	X	X	X	X					X
Sampling for pGSN levels (including PK) j		X	X	X k	X	X	X	X	X
CBC with differential and reticulocyte count; PT (INR)/aPTT e	X	X b	X	X	X	X	X	X	X
Comprehensive metabolic profile (including amylase or lipase) e	X	X b	X	X	X	X	X	X	X
Biomarker sampling l		X		X	X	X	X	X	
Anti-rhu-pGSN antibody sampling (immunogenicity) m		X					X		X
Study drug administration n		X o	X p						
AEs/SAEs q	X	X	X	X	X	X	X	X	X
Con meds	X	X	X	X	X	X	X	X	X

Abbreviations: AEs=adverse events; CBC=complete blood count; Con meds=concomitant medications; CRP=C-reactive protein; CT=computed tomography; CURB-65=Confusion, Urea >7 mmol/L, Respiratory rate ≥ 30/min, Blood pressure systolic <90 or diastolic ≥60, and age ≥65 years (score); CXR=chest x-ray; EKG=electrocardiogram; HIV=human immunodeficiency virus; IL=interleukin; INR=international normalized ratio; PEEP=positive end-expiratory pressure; PK=pharmacokinetic; PT=prothrombin time; aPTT=activated partial thromboplastin time; RT-PCR=reverse transcription polymerase chain reaction; SOC=standard of care; Term=termination; TNF=tumor necrosis factor; WHO=World Health Organization.

a Day 1 is the first day of study treatment. Baseline tests (including blood draws) should be performed prior to administration of the first dose. Screening tests may also be performed on Day 1 prior to study treatment if necessary, as long as these tests cannot affect eligibility. If Dose 1 is administered in the evening of Day 1, Dose 2 would be given on the second calendar day and Dose 3 would be given on the third calendar day,

b Test/assessment does not have to be repeated if performed within the prior 24 hours unless dictated by SOC.

c Assess daily from screening through Day 14 during hospitalization and after discharge, where feasible, and then at Days 28, 60, and 90.

d Collect sputum sample as soon as possible if not collected at the time of hospital admission. The microbiology lab is encouraged to also perform sputum Gram-stains, antigen detection, immunoassay, and RT-PCR diagnostic tests when available. If fevers or chills are present, 2 sets of blood cultures are recommended at the discretion of the caregivers.

e To be performed if/when indicated by SOC.

f At screening, document radiographic evidence (CXR, or CT scan if CXR is inadequate) of COVID-19 pneumonia if not already completed in the previous 48 hours per SOC. On Days 14 and 28, repeat RT-PCR for COVID-19 and repeat CXR, or CT scan if CXR is inadequate, are encouraged but not mandatory.

g Height and weight only to be measured at screening or baseline and as per SOC thereafter. In Part 2, height is not required at screening and weight may be obtained via bed scale, if possible, or estimated.

h Record blood pressure, body temperature, respiration rate, and heart rate, as well as pulse oximetry. In Part 2, while the subject is intubated, the respiratory rate and the ventilator settings (i.e., tidal volume, inspired oxygen, inspiratory pressure, and PEEP) should be documented. To be measured during study drug administration at the following time points: predose, at the end of administration, and 30 minutes after the end of administration.

i When EKGs are to be collected at the same time point as a blood collection, EKGs should be collected first. At screening, 3 serial, resting, supine 12-lead EKGs are to be conducted within 10 minutes total time. All other ECGs are single recordings.

j Blood for PK will be drawn for Dose #1 within 15 minutes predose, and at 1 ( $\pm 15$  min), 2 ( $\pm 15$  min), 6 ( $\pm 30$  min), and 12 ( $\pm 30$  min) hours after the end of administration (but prior to Dose #2); and for Dose #3 within 15 minutes predose, and at 1 ( $\pm 15$  min), 2 ( $\pm 15$  min), 6 ( $\pm 30$  min), 12 ( $\pm 30$  min), and 24 ( $\pm 30$  min) hours after the end of administration. Samples should be spun and plasma frozen and sent to a central lab for analysis.

k Blood for PK will be collected 24 hours after the end of study drug administration given on Day 2 so the last sample will be obtained Day 3.

 Collect blood for measurement of ferritin, D-dimer, CRP, and procalcitonin for evaluation at local laboratory; save an approximate 10 mL aliquot of blood plasma or serum to be frozen at -20°C for subsequent biomarker assays (likely to include, but not limited to IL1, IL6, IL10, TNF, etc.) for analysis at the central laboratory.

m Sample to be sent to a central lab for analysis.

n Study drug to be administered at 0, 12, and 36 hours ( $\pm$  60 minutes). Subjects are to be monitored for administration site reactions during study drug administration and for 1 hour after its completion.

o Initial dose must be administered no later than 12 hours after randomization. A second dose on Day 1 is to be administered 12 hours after the initial dose.

p Day 2 dose to be administered 24 hours after last dose administration on Day 1 (36 hours after Dose #1).

q From informed consent to first administration of study drug, AEs related to study procedures and all SAEs will be recorded. During and after first administration of study drug, all AEs and SAEs will be recorded through Day 14. After Day 14, only SAEs will be recorded through study completion.

## **9.1. Screening Assessments**

Potential subjects hospitalized with COVID-19 pneumonia will be screened for Part 1 within 24 hours of reaching a WHO severity score of 4 to 6, whether the severity score is attained on admission or during hospitalization, or for Part 2, within 24 hours of intubation without ECMO with a WHO severity score of 6 or 7.

Prior to screening, all subjects/next of kin/legal proxy must provide informed consent for study participation, per [Section 13.5](#). The following assessments will be performed according to the time points in the Schedule of Assessments ([Table 5](#)).

### **9.1.1. WHO Severity Score**

During screening and at the time points presented in the Schedule of Assessments ([Table 5](#)), each subject's WHO severity score according to the 9-point scale (Section [6.1](#)) will be recorded on the appropriate eCRF. WHO severity scores should be documented daily through Day 14 (during hospitalization and after discharge, where feasible).

### **9.1.2. HIV Testing**

Subjects are not required to have a negative serology test for HIV to participate in the study. Testing is not required but could be done as part of SOC at the discretion of caregivers.

### **9.1.3. Confirmation of COVID-19 Pneumonia**

Subjects are required to have pneumonia (confirmed clinically and documented on CXR or CT), with RT-PCR+ confirmed or highly suspected COVID-19 etiology at screening. If documentation is not available, the subject must undergo CXR, or a CT scan if CXR is inadequate, to confirm COVID-19 pneumonia. At screening, radiographic evidence (CXR, or CT scan) of COVID-19 pneumonia may have been completed in the previous 48 hours per SOC. If not already obtained and documented during the current illness leading to the present hospitalization, a RT-PCR test is to be performed during screening before randomization (result might not be available at randomization or start of study treatment).

On Days 14 and 28, repeat RT-PCR for COVID-19 and repeat CXR, or CT scan if CXR is inadequate, are encouraged but not mandatory.

### **9.1.4. Pregnancy Test**

All females of childbearing potential are required to have a negative serum or urine pregnancy test at screening to participate in the study.

## **9.2. Safety Assessments**

The following assessments will be performed according to the time points in the Schedule of Assessments ([Table 5](#)).

### **9.2.1. Demographic/Medical History**

A review of demographic parameters, including age, gender, race, and ethnicity will be performed at screening.

Relevant past and present medical history will be recorded. Any ongoing condition or signs and symptoms observed prior to the initiation of study treatment should be recorded as medical history.

#### **9.2.2. Vital Signs**

Vital signs will include blood pressure, body temperature, respiration rate, and heart rate, as well as pulse oximetry. In Part 2, while the subject is intubated, the respiratory rate and the ventilator settings (i.e., tidal volume, inspired oxygen, inspiratory pressure, and PEEP) should be documented. Vitals signs will be measured during study drug administration at the following time points: predose, at the end of administration, and 30 minutes after the end of administration. Significant findings noticed after the start of study drug that meet the definition of an AE must be recorded in the eCRF.

#### **9.2.3. Physical Examination**

All PEs, including measurement of body weight, will be performed by a study physician or designee. In Part 1, height and weight need only be measured at screening or baseline. In Part 2, height is not required at screening and weight may be obtained via bed scale, if possible, or estimated. The initial body weight measured at enrollment will be used to calculate rhu-pGSN dosing for all doses (so that an individual subject will always receive the same dose). Body weight can be repeated per SOC thereafter where possible. The physical examination includes skin, head, ears, eyes, nose, throat, heart, lungs, abdomen, and neurologic system, where possible. Additional examination may be performed as found relevant by the Investigator.

#### **9.2.4. Outcome Prediction Models**

The CURB-65 ([Appendix A](#)) test will be utilized at screening. The cognitive status of the subject will be assessed for incorporation in the CURB-65 score by using the abbreviated mental test score; [Appendix B](#).

#### **9.2.5. Electrocardiogram**

All EKGs will be conducted and read locally. When EKGs are to be collected at the same time point as a blood collection, EKGs should be collected first. At screening, 3 serial, resting, supine, 12-lead EKGs will be conducted within 10 minutes total time. The mean of the triplicate EKG measurements performed at screening will serve as the subject's baseline corrected QT (QTc) value for all post-dose comparisons. All other ECGs will be collected as a single recording.

EKG parameters to be evaluated include heart rate, the time from the onset of the P wave to the start of the QRS complex (PR), the duration of the entire cardiac cycle, measured in seconds (RR), the combination of three of the graphical deflections (QRS complex), the measure of the time between the start of the Q wave and the end of the T wave (QT) intervals, and the QT interval corrected for heart rate using Fridericia's formula (QTcF).

### **9.2.6.      Laboratory Assessments**

All routine clinical laboratory assessments will be performed by the hospital laboratory or equivalent per SOC. Where indicated, handling and shipping clinical laboratory samples to a central laboratory will be outlined in the Laboratory Manual.

Screening laboratory and other tests can serve as baseline values for participants, they do not need to be repeated if performed within the prior 24 hours of randomization unless otherwise dictated by SOC; however, the blood sample for analysis of pGSN antibodies must be repeated if not collected within 30 minutes of initiating the first dose of study drug.

The laboratory evaluations will include:

1. Hematology: complete blood count with differential white count and reticulocyte count, and platelet count; PT (INR)/aPTT
2. Comprehensive metabolic profile including chemistries/electrolytes, total protein/albumin, blood urea nitrogen (BUN)/creatinine, CRP, lactate dehydrogenase (LDH), creatine phosphokinase (CPK), alanine aminotransferase (ALT), aspartate aminotransferase (AST), total bilirubin, total cholesterol, low-density lipoprotein (LDL) cholesterol, high-density lipoprotein (HDL) cholesterol, alkaline phosphatase, and amylase or lipase
3. Respiratory function (oxygen saturation by pulse oximetry; arterial blood gas tests only at the caregiver's discretion)

Abnormal laboratory test results considered clinically significant by the Investigator or that require treatment should be reported as AEs in the eCRF according to the AE reporting instructions in [Section 10.6](#).

### **9.3.      Pharmacokinetic Assessments**

Blood for PK will be drawn at the following time points:

- For Dose #1: within 15 minutes predose, and at 1 ( $\pm 15$  min), 2 ( $\pm 15$  min), 6 ( $\pm 30$  min), and 12 ( $\pm 30$  min) hours after the end of dose administration (but prior to Dose #2)
- For Dose #3: within 15 minutes predose, and at 1 ( $\pm 15$  min), 2 ( $\pm 15$  min), 6 ( $\pm 30$  min), 12 ( $\pm 30$  min) and 24 ( $\pm 30$  min) hours after the end of dose administration

Samples should be spun and plasma frozen and sent to a central lab for analysis. Plasma samples will be analyzed for maximum concentration ( $C_{max}$ ), time to maximum concentration ( $T_{max}$ ), terminal half-life ( $T_{1/2}$ ), area under the curve from time zero to 8 hours ( $AUC_{0-8}$ ), area under the curve from time 0 to infinity ( $AUC_{inf}$ ).

Participants who refuse some or all PK blood samplings can remain in the trial. However, PK sampling is to be highly encouraged.

For Dose #3, the last PK sample will occur on Day 3 (i.e., 24 hours after the end of third study drug administration which was initiated 36 hours after the first dose).

#### **9.4. Pharmacodynamic Assessments**

On the study days indicated in [Table 5](#), blood will be collected for measurement of ferritin, D-dimer, CRP, and procalcitonin level at local laboratory. Save aliquots of blood for subsequent analysis. Analyses are likely to include, but are not limited to, the following:

- Biomarkers including, but not limited to, IL1, IL6, IL10, TNF, etc. (see [Table 5](#) Schedule of Assessments and footnote 'I' for details).

Blood samples may be stored for analysis for up to 5 years in the event that new biomarkers are discovered.

#### **9.5. Other Assessments**

Other analyses to be performed include:

- Blood, sputum, and other cultures as clinically indicated per SOC (note that a sputum culture is mandatory if a sputum specimen can be obtained and blood cultures are strongly encouraged at entry into the study)

## **10. ADVERSE EVENT MANAGEMENT**

### **10.1. Definition of Adverse Events**

#### **10.1.1. Adverse Event (AE)**

An AE is the development of an undesirable medical condition or the deterioration of a pre-existing medical condition following or during exposure to a pharmaceutical product, whether or not considered casually related to the product.

All AEs that occur during or after a subject has been administered study drug, or within 14 days following the last study drug administration, whether or not they are related to the study, must be recorded on forms provided by the Sponsor.

#### **10.1.2. Serious Adverse Event (SAE)**

An SAE is an AE occurring during any study phase (i.e., baseline, treatment, or follow up), and at any dose of the investigational product, comparator or placebo, that fulfills one or more of the following:

- Results in death
- It is immediately life-threatening
- It requires in-patient hospitalization or prolongation of existing hospitalization
- It results in persistent or significant disability or incapacity
- Results in a congenital abnormality or birth defect
- It is an important medical event that may jeopardize the subject or may require medical intervention to prevent one of the outcomes listed above.

All SAEs that occur after the subject/next of kin/legal proxy has given informed consent and has been randomized, including before or during treatment and within 90 days following the last dose of study drug, whether or not judged to be related to the study, must be recorded on forms provided by the Sponsor.

### **10.2. Clarifications to Serious Adverse Event Reporting**

Death is an outcome of an SAE and not an SAE in itself. When death is an outcome, report the event(s) resulting in death as the SAE term (e.g., “pulmonary embolism”). If the cause of death is unknown, report “Death, unknown cause” as the SAE term.

### **10.3. Assessment of Causality**

The relationship of each AE to the study drug administration will be assessed by the Investigator after careful consideration of all relevant factors such as (but not limited to) the underlying study indication, coexisting disease, concomitant medication, relevant history, pattern of the AE, temporal relationship to receipt of the study medication and de-challenge or re-challenge according to the following guidelines:

YES (possible, probably or definitely related): there is a reasonable possibility that the study drug caused the event; one or more of the following criteria apply:

- The event follows a reasonable temporal sequence from administration of study drug.
- The event could not be reasonably attributed to the known characteristics of the subject's clinical state, environment or toxic factors or other modes of therapy administered to the subject.
- The event follows a known pattern of response to study drug.
- The event disappears or decreases on cessation or reduction in dose of the study drug. In some situations, an AE will not disappear or decrease in intensity upon discontinuation of the study drug despite other clear indications of relatedness.

NO (probably not related or definitely not related): There is no reasonable possibility that the study drug caused the event and none of the criteria from the previous section apply; one or more of the following criteria apply:

- The event does not follow a reasonable temporal sequence from administration of study drug.
- The event could be reasonably attributed to the known characteristics of the subject's clinical state, concurrent illness, environment or toxic factor or other modes of therapy administered to the subject.
- The event does not follow a known pattern of response to study drug.
- The event does not disappear or decrease on cessation or reduction in dose of the study drug, and it does not reappear or worsen when the study drug is re-administered.

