## **6.2. Data and Safety Monitoring Board**

An independent DSMB will be established to closely monitor the safety of subjects. The primary mission of the DSMB is to ensure that decisions are made that serve the best interests of patients volunteering for the study.

The independent DSMB will be comprised of 4 voting members: 3 academicians/clinicians with expertise in pulmonary care, critical care, and/or infectious diseases as related to COVID-19 pneumonia, and a statistician. Representatives from the Contract Research Organization (CRO) and Sponsor's Chief Medical Officer will be able to attend the open meetings to provide information and administrative support to the DSMB. However, they will not have any voting rights and will not attend the closed meeting where unblinded data may be discussed.

No SAEs have been associated with the investigational medicinal product. Thus, all SAEs will be considered as unexpected for reporting purposes. All reported deaths and treatment-emergent SAEs will be sent by EastHORN Safety to the DSMB within 2 working days of notification of the CRO/Sponsor by the sites. The events will be evaluated by the DSMB and comments returned to EastHORN Safety within 2 working days of notification of the DSMB. A DSMB meeting does not necessarily need to be convened. Ad hoc meetings will be convened whenever felt appropriate by a DSMB member.

In Part 1, periodic safety reviews will be conducted after 12, 24, 36, and 48 subjects have been fully dosed and completed assessment at Day 14. Only DSMB members will be provided with partially unblinded results separated into 2 groups by treatment without identifying the actual treatment. If all participants have completed study therapy before the last DSMB meeting involving review of 48 subjects after their Day 14 visit can be held, this meeting can be cancelled at the discretion of the DSMB chair.

Data may be further unblinded and/or the study paused at the discretion of the DSMB chair; otherwise, enrollment will continue during the safety review.

Please refer to the DSMB Charter for further details.

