## **10.7. Reporting Adverse Events**

All AEs, serious and nonserious, will be fully documented on the appropriate eCRF. For each AE, the Investigator must provide its duration (start and end dates or ongoing), intensity, assessment of causality and whether specific action or therapy was required.

All AEs that occur from informed consent until the first dose of study drug should be recorded on the AE eCRF page only if the event was related to a study procedure. All other AEs/findings prior to first dose of study drug should be recorded as medical history on the applicable eCRF page. AEs occurring from the first dose of study drug until 14 days after the last dose of study drug must be recorded on the AE eCRF. An ongoing AE identified prior to 14 days after the last study drug administration will be followed if possible until resolution.

All SAEs occurring any time (baseline, treatment, or follow up) during the study (related or unrelated) must be reported to EastHORN Safety within 24 hours of the Investigator's knowledge. This should be done in accordance with the instructions on SAE Report Form completion and reporting

Investigators must follow subjects with AEs/SAEs until the event has resolved, the condition has stabilized, withdrawal of consent, the subject is lost to follow up or death OR until the EOS Visit, whichever occurs first. An ongoing SAE identified by EOS will be followed if possible until resolution. If the subject dies, this should be captured as the outcome of the AE unless no link between the AE and the subject death can be established, in which case the AE will be marked as ongoing and the death will be reported as a separate event.

If a subject is lost to follow up, this should be captured accordingly within the AE eCRF and on the follow up SAE report.

The Sponsor or designee is responsible for notifying the relevant regulatory authorities of applicable suspected unexpected serious adverse reactions (SUSARs) as individual notifications or through periodic line listings. It is the PI's responsibility to notify the Institutional Review Board (IRB) or IEC of all SAEs that occur at his or her site according to the local regulations. Investigators will also be notified of all unexpected, serious, drug-related events (7/15 Day Safety Reports) that occur during the clinical trial.

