11.12 Adverse Events

A Treatment-Emergent Adverse Event (TEAE) is defined as any AE that begins/ worsens after the first IMP administration.

Related Adverse Events include Possibly, Probably and Definitely Related Adverse Events. Not Related Adverse Events include Probably and Definitely not related Adverse Events.

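### Protocol 10.3 rules out NO whenever any YES criterion applies, so an event that is well timed but explained by COVID-19 is either YES or has no category

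*Protocol*

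**What the plan says.** Protocol section 10.3 says that the relationship of each AE to study drug "will be assessed by the Investigator after careful consideration of all relevant factors such as (but not limited to) the underlying study indication". It goes on to name coexisting disease, timing and dechallenge among other factors, and calls the two lists that follow guidelines.

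- **YES** is headed by a reasonable possibility of causation and needs at least one of four criteria. The first is "The event follows a reasonable temporal sequence from administration of study drug". The fourth is "The event disappears or decreases on cessation or reduction in dose of the study drug".
- **NO** is headed "There is no reasonable possibility that the study drug caused the event and none of the criteria from the previous section apply", and also needs at least one of four NO criteria. The second of these begins "The event could be reasonably attributed to the known characteristics of the" and goes on to name the subject's clinical state and concurrent illness.

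Neither document says how to rate an event that meets a criterion in each list, or whether reaching the planned end of dosing counts as cessation.

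Causality of AEs is part of a secondary safety endpoint (Protocol 5.2.2). SAP 11.12 splits it in two: "Related Adverse Events include Possibly, Probably and Definitely Related Adverse Events", with the two remaining levels counted as not related. SAP 12.10.1.1 to 12.10.1.3 tabulate related TEAEs, related serious TEAEs, Grade 3 or higher related AEs, and AEs by relationship and intensity. On reporting, Protocol 6.2 states "Thus, all SAEs will be considered as unexpected for reporting purposes", and Protocol 10.7 states "Investigators will also be notified of all unexpected, serious, drug-related events (7/15 Day Safety Reports) that occur during the clinical trial".

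**The concern.** In this population the usual reason to call an event unrelated is that COVID-19 explains it. Section 10.3 lists that reason under NO, but a single YES criterion cancels it, and plausible timing is a YES criterion. The dosing course is short: the third and last dose is given 36 hours after the first (Protocol 6.5), while AEs are recorded until 14 days after the last dose (Protocol 10.7). Many disease events will therefore follow dosing closely, and most that resolve will do so once dosing is over.

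Three things are at stake: the related-AE counts within each arm, agreement between raters on the same kind of event, and the number of disease events that qualify as unexpected, serious and drug-related.

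**Working it through.** Section 10.3 states no figure to reproduce. The check is logical, followed by one illustration under assumed rates.

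**1. The conditions side by side.** T = reasonable timing, U = not reasonably attributable to clinical state or other therapy, K = known pattern, D = improves on cessation or dose reduction, R = reasonable possibility.

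- YES, reading A: at least one of T, U, K, D is enough.
- YES, reading B: R and at least one of T, U, K, D.
- NO: not R, and none of T, U, K, D, and at least one NO criterion.

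The first three NO criteria are the negations of T, U and K. When no YES criterion applies they hold automatically, so the NO list adds nothing to the exclusion clause. Attribution to COVID-19 (not U) can never support NO on its own.

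**2. An example.** Respiratory failure on Day 3 that the Investigator puts down to COVID-19: T present, U and K absent, R absent. NO is barred because T is present. Reading A gives YES. Under reading B the event is neither YES nor NO. If it later resolves, D may also be claimed, because the text does not separate the planned end of dosing from cessation.

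**3. All profiles.** Four criteria and R give 2^5 = 32 profiles.

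| Reading | YES | NO | Neither |
|---|---|---|---|
| A: one criterion is enough | 30 | 1 | 1 |
| B: criterion and reasonable possibility | 15 | 1 | 16 |

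The single NO profile is T, U, K, D and R all absent. Under B, 15 of the 16 unclassified profiles have a YES criterion met although the Investigator sees no reasonable possibility. The other has a reasonable possibility but no criterion. These counts show how narrow NO is; they are not event frequencies.

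**4. Is deleting the clause enough?** Without it, of the 2^4 = 16 criterion profiles only all-present is purely YES and only all-absent is purely NO. The other 16 − 2 = 14 meet both lists. (This takes the fourth NO criterion as the negation of D; its rechallenge half could move one profile at most.) Deletion alone leaves no rule for mixed profiles, so the text must also say what decides.

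**5. Effect on the between-arm contrast.** Assumptions, not in the documents: the drug truly causes an event in x = 15% of active subjects, independently of a background event rate b that is equal in both arms, and every background event is rated related (the worst case, reading A).

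- Active arm rated related = 1 − (1 − b)(1 − x); placebo = b.
- Difference = x(1 − b).
- Share of active-arm related subjects in excess of background = x(1 − b) / [1 − (1 − b)(1 − x)].

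| b | Active | Placebo | Difference (points) | Excess share |
|---|---|---|---|---|
| 0% | 15.0% | 0% | 15.0 | 100% |
| 5% | 19.25% | 5% | 14.25 | 74% |
| 20% | 32.0% | 20% | 12.0 | 37.5% |
| 40% | 49.0% | 40% | 9.0 | 18% |
| 60% | 66.0% | 60% | 6.0 | 9% |

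The within-arm related count degrades fast. The difference between arms shrinks more slowly and does not vanish.

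**6. Reporting.** Because every SAE is treated as unexpected (Protocol 6.2), an SAE rated YES on timing alone meets the wording of the notification sentence in Protocol 10.7, in saline recipients as well as active ones.

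**The case against.** The strongest reply is that the lists are only guidelines under a judgement that expressly weighs the study indication and coexisting disease, and that the timing criterion says *reasonable* sequence, not merely after dosing. Both are right. A reader might infer that every COVID-19 event is forced to related; the documents do not support that. A late event that meets no YES criterion can still be NO, and many Investigators will simply use their judgement. But the NO condition is an explicit conjunction, and nothing gives the judgement priority over it. The likelier result is ratings that vary with the reader.

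On dechallenge, treating recovery after a completed course as cessation is one reading and is not compelled. It stands as an ambiguity. The timing criterion carries the point without it.

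A reader might also infer that the related-AE tables nearly duplicate the all-TEAE tables and carry almost no information. That needs reading A and a YES criterion met by almost every background event, and the documents settle neither. The same rule is applied blind in both randomised arms, so the contrast survives in diluted form. SAP 11.12 names five levels and SAP 12.10.1.1 also tabulates by relationship, so some gradation may remain.

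It is tempting to multiply the planning proportions of 20% and 5% by 30 per arm and read the result as a number of misrated SAEs. Day 14 endpoint failures are not related SAEs. They include early discontinuation and inconclusive status (SAP 12.9.1.1), and conditions present before treatment are recorded as medical history (Protocol 9.2.1).

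Safety oversight does not hang on this rating. All SAEs are reported within 24 hours whether related or not (Protocol 10.7), and deaths and treatment-emergent SAEs go to the DSMB (Protocol 6.2). With a safety database of 24 recipients (Protocol 4.7.1), leaning towards over-inclusion is defensible. That argues against making attribution to COVID-19 sufficient for NO. It does not defend a rule that can leave an event with no category.

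**Conclusion.** The point holds as a wording defect in Protocol 10.3. On the literal text, a reasonably timed event explained by COVID-19 cannot be rated NO: it is YES, or unclassified if YES also needs a reasonable possibility. NO is open in 1 of 32 profiles. Within-arm related counts will be inflated or inconsistent, and some disease-related SAEs may become candidates for expedited notification.

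The between-arm contrast is weakened, not removed; the size in the table rests on assumed rates and on the worst-case reading. SAE incidence, the primary safety endpoint (Protocol 5.2.1), has no causality component and is untouched. The documents give no basis for a count of affected events. This should be corrected, but it does not threaten the trial's main conclusions.

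**What to change.** In Protocol 10.3:

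- Delete from the NO heading the condition that no YES criterion applies.
- State that the overall reasonable-possibility judgement decides YES or NO and that the listed criteria only support it, including when an event meets criteria in both lists.
- State that timing alone does not oblige a YES.
- State that resolution after the planned last dose is not by itself positive dechallenge.

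Do not make attribution to COVID-19 sufficient for NO; in this population that would let almost any event be rated unrelated.

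The cost is a change to the protocol and eCRF-guideline wording. For events already recorded, send blinded queries before database lock, limited to those where the rating conflicts with the Investigator's overall judgement. The blinded review in SAP 9.4 is a natural place to close them.
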